**MGC018 Overall Study Design**

**Note:** MTD-2 = the dose level that is 2 dose levels below the MTD defined for MGC018 monotherapy.

[figure not shown]
MTD-1 = the dose level that is 1 dose level below the MTD defined for MGC018 monotherapy.

**Abbreviations:** mCRPC = metastatic castrate-resistant prostate carcinoma; MTD = maximum tolerated dose; NSCLC = non-small cell lung cancer; Q3W = every 3 weeks; RP2D = recommended phase II dose; SCCHN = squamous cell carcinoma of the head and neck; TBD = to be determined; TNBC = triple negative breast cancer.

MGC018 will be administered alone or in combination with MGA012 (also known as INCMGA00012), as illustrated below in [Figure 6](#) and [Figure 7](#), respectively. For Module A, MGC018 alone will be administered IV over 60 minutes on Days 1 and 22 of Cycle 1 and every subsequent 42-day cycle thereafter. For Module B, MGC018 alone will be administered IV over 60 minutes on Day 1 of Cycle 1 and with MGA012 on Day 22 of Cycle 1. Both MGC018 and MGA012 will be administered on Days 1 and 22 of every subsequent 42-day cycle thereafter, at the assigned dose for each cohort. Similar to MGC018, MGA012 will be administered IV over 60 minutes. On days when the MGC018 and MGA012 are to be administered on the same day (Module B only), MGA012 should be given first, followed immediately thereafter by MGC018.

**Figure 6**

[figure not shown]
**MGC018 Monotherapy Dosing Schedule (Q3W) (Module A)**

**Note: Imaging for tumor assessments will be every 9 weeks (63 days) during the Cohort Expansion Phase for Module A.**

**Figure 7**

**MGC018 and MGA012 Combination Dosing Schedule (Q3W) (Module B)**

For both the Dose Escalation Phase of Module A and Module B and the Cohort Expansion Phase of Module B, tumor assessments will occur at Day 42 of each cycle, for the first 4 cycles, and every other cycle thereafter. For the Cohort Expansion Phase of Module A, the tumor assessments will occur every 9 weeks (63 days). For Module A, the DLT evaluation period will be 21 days in duration; for Module B, the DLT evaluation period will be 42 days in duration (see [Section 4.1.1](#) below for more details). Participants who complete a given cycle, remain clinically stable, do not experience a DLT or other unacceptable toxicity, and do not otherwise meet the criteria for permanent treatment discontinuation may be eligible for additional treatment with MGC018 alone or in combination with MGA012 for up to a total of 18 cycles (approximately 2 years). For participants with a dose delay > 21 days, the total number of cycles may be < 18 cycles and the time on MGC018 will be no more than 2 years.

Following the last dose of study drug, all participants in Module A and Module B Cohort Expansion Phases will be followed every 3 months (90 days) for survival during a 2-year Survival Follow-up Period, until criteria are met for study discontinuation. Participants in Module A Dose Escalation Phase will be followed similarly for survival status until approval of Amendment 3, at which point they will be discontinued from follow up.

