## 9.17 Post-Treatment Follow-up Visit

The Post-Treatment Follow-up period includes the following:

- Survival follow-up for participants in the Cohort Expansion Phase of Module A or Module B: approximately a 2-year period for each participant following the last dose of MGC018; this period runs until the last participant in the study completes his/her survival follow-up period. Participants in Module A Dose Escalation will be followed for survival status until approval of Amendment 3, at which point they will be discontinued from follow up.
- During this time, participants will be followed via clinic visit, telephone, paper mail, or other electronic contact at 3-month (90 days) intervals for follow-up of OS.
- For mCRPC participants, serum testosterone and PSA will be collected approximately every 12 weeks during the follow-up period until disease progression, start of another cancer therapy, or the study cutoff date, whichever comes first.
- Response status: information regarding response status and/or the occurrence of disease progression may be collected every 3 months (90 days) on all participants who discontinued from study treatment due to reasons other than PD, if they have not initiated any other cancer-directed therapy. Tumor response results (e.g., CT imaging results) may be entered in the electronic data capture (EDC) system if available per standard of care procedures to document the date of progression.

Post-Treatment Follow-up is performed until the end of study for each participant. Survival follow-up will be discontinued for participants enrolled in Module A Dose Escalation Phase after the approval of Amendment 3.

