#### 11.1.2 Survival Assessments

Participants who are discontinued from study treatment in the Cohort Expansion Phase of Module A or Module B will be followed for survival status every 3 months (90 days) for a 2-year survival follow-up period following the last dose of MGC018 alone (Module A) or in combination with MGA012 (Module B), or until the event of death, they withdraw consent, or are lost to follow-up (see [Section 9.17](#)). Survival follow-up will be discontinued for participants enrolled in Module A Dose Escalation after the approval of Amendment 3.

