**Module B Dose Escalation and Cohort Expansion Phases**

| EVALUATION/
PROCEDURE                                                                                                                                                                                                                                                                                                                                                                                                                                                                          | Screening 
(Within 28 days) | Cycle 1 |              |                |        |                 |                                | Cycle 2 and subsequent Cycles  |                 |                                 |                 | End of
Treatment
Visit  | Post
TRT
FUP |
|---------------------------------------------------------------------------------------------------------------------------------------------------------------------------------------------------------------------------------------------------------------------------------------------------------------------------------------------------------------------------------------------------------------------------------------------------------------------------------------------------|----------------------------------------------|---------|--------------|----------------|--------|-----------------|--------------------------------|----------------------------------------------|-----------------|---------------------------------|-----------------|---------------------------------------------|--------------------|

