| Survival Follow-up                                                                                                                                                                                                                                                                                                                                                                                                                                                                                |                                              |         |              |                |        |                 |                                |                                              |                 |                                 |                 |                                             | X                  |
| Survival follow-up collected every 3 months (90 days ± 7 days) by clinic visit, telephone, paper mail, or other electronic contact for 2 years; information regarding response status and/or the occurrence of disease progression may be collected approximately every 3 months in participants who discontinued from study treatment due to reasons other than progressive disease, if they have not initiated any other cancer directed therapy. See Section 9.17 for details. |                                              |         |              |                |        |                 |                                |                                              |                 |                                 |                 |                                             |                    |

- 1 The Screening visit should occur within 28 days prior to Day 1.
- 2 Cycle 1 Day 42 and Cycle 2 Day 1 may be combined. Regardless if the visits are combined or not, Cycle 1 Day 42 assessments should occur before Cycle 2 Day 1 assessments. The same applies to all consecutive cycles.
- 3 Evaluations/procedures performed on Days 23, 25, 29, and 36 apply to Cycle 2 only.
- 4 The EOTV should be performed within 30 days following the last dose of study drug.

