For both the Dose Escalation Phase of Module A and Module B and the Cohort Expansion Phase of Module B, tumor assessments will occur at Day 42 of each cycle, for the first 4 cycles, and every other cycle thereafter. For the Cohort Expansion Phase of Module A, the tumor assessments will occur every 9 weeks (63 days). For Module A, the DLT evaluation period will be 21 days in duration; for Module B, the DLT evaluation period will be 42 days in duration. Participants who complete a given cycle, remain clinically stable, do not experience a DLT or other unacceptable toxicity, and do not otherwise meet the criteria for permanent treatment discontinuation may be eligible for additional treatment with MGC018 alone or in combination with MGA012 for up to a total of 18 cycles (approximately 2 years).

Following the last dose of study drug, all participants in Module A and Module B Cohort Expansion Phases will be followed every 3 months (90 days) for survival during a 2-year Survival Follow-up Period, until criteria are met for study discontinuation. Participants in Module A Dose Escalation Phase will be followed similarly for survival status until approval of Amendment 3, at which point they will be discontinued from follow up.

Figure 1

[figure not shown]
[figure not shown]
Overall Study Design

Note: MTD-2 = the dose level that is 2 dose levels below the MTD defined for MGC018 monotherapy.

MTD-1 = the dose level that is 1 dose level below the MTD defined for MGC018 monotherapy.

Abbreviations: mCRPC = metastatic castrate-resistant prostate carcinoma; MTD = maximum tolerated dose; NSCLC = non-small cell lung cancer; Q3W = every 3 weeks; RP2D = recommended phase II dose; SCCHN = squamous cell carcinoma of the head and neck; TBD = to be determined; TNBC = triple negative breast cancer.

Figure 2**MGC018 Monotherapy Dosing Schedule (Module A)****Figure 3****MGC018 and MGA012 Combination Dosing Schedule (Module B)**

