6 STATISTICAL METHODOLOGY

6.1 General Considerations

Safety and efficacy summaries will be provided for each dose level cohort during dose escalation and for all dose level cohorts combined, as well as for expansion cohorts where appropriate. Response rates will be calculated for the response evaluable population.

Unless otherwise specified, the following general considerations are applied in data analyses:

- The baseline value is defined as the latest value on or prior to the first dose of study treatment.
- Categorical data will be summarized by the number and percent of participants falling within each category.
- Continuous variables will be summarized by descriptive statistics, including mean, standard deviation, median, minimum, and maximum.
- Time-to-event endpoints will be summarized by the number and percent of the event, median time and corresponding 95% confidence interval (CI), and event free rate and corresponding 95% CI at the specified time points of interest.
- The impact of COVID-19 may be assessed and analyzed on a case-by-case basis. In particular, the following analyses may be performed if there are enough COVID-19 positive participants to render the analyses meaningful:
 - Number of participants discontinued study treatment and/or discontinued from study due to COVID-19, if such a reason is collected
 - Summary of tumor response, PFS, rPFS and OS
 - Summary of study drug interruption, delay or withdrawal due to COVID-19, if such a reason is collected
 - Listing of protocol deviations due to COVID-19
- All data summaries and tabulations will be conducted using SAS® software Version 9.4 or higher.

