6.7.2.3 Analyses of Overall Survival

The Kaplan-Meier method will be applied to estimate OS curve, median OS, and OS rates at 6 and 12 months. For patients who are not known to be dead at the time of data cut-off for OS analysis, the OS will be censored at the time they are last known to be alive. The method of Brookmeyer and Crowley ([1](#)) will be used to construct 95% CI for median OS. The 95% CIs for OS rate at 6 and 12 months will be calculated by normal approximation after log(-log) transformation. OS will be analyzed by tumor type when sample size warrants.

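### The documents disagree on whether Module B dose-escalation participants have survival follow-up; under the body text, the planned OS rates for that phase are probably too high

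*Protocol*

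**What the plan says.** Protocol 4.1 states that "all participants in Module A and Module B Cohort Expansion Phases will be followed every 3 months (90 days) for survival" during a 2-year period after the last dose. SAP 3.1 repeats this. Both synopsis entries (study design and survival assessments) have the same scope. Protocol 9.17 describes "Survival follow-up for participants in the Cohort Expansion Phase of Module A or Module B", and 11.1.2 says "Participants who are discontinued from study treatment in the Cohort Expansion Phase of Module A or Module B will be followed for survival status".

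Module A dose escalation is handled separately and consistently. SAP 3.1 reads: "Participants in Module A Dose Escalation Phase will be followed similarly for survival status until approval of Amendment 3". After that date these participants are dropped from follow-up. None of these places mentions Module B dose escalation.

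Appendix 1 has one schedule headed "Module B Dose Escalation and Cohort Expansion Phases". Its survival row reads "Survival follow-up collected every 3 months (90 days ± 7 days) by clinic visit, telephone, paper mail, or other electronic contact for 2 years", with no limit to expansion, and refers to 9.17 for details.

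On analysis, OS is an exploratory objective for both modules and uses the Safety Population (SAP 2.3, 4.1). SAP 6.1 says "Safety and efficacy summaries will be provided for each dose level cohort during dose escalation and for all dose level cohorts combined". SAP 6.7.2.3 plans Kaplan-Meier OS rates at 6 and 12 months. For those not known to be dead, "the OS will be censored at the time they are last known to be alive".

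**The concern.** A site cannot satisfy both texts for a Module B escalation participant who has stopped treatment. Appendix 1 asks for quarterly contact for 2 years. The section it cites for details covers expansion only.

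The choice reaches a planned analysis. If post-treatment contact is not made, the last date known alive falls near the end-of-treatment visit or the end of the 30-day adverse-event window. Progression is a listed reason for stopping (Protocol 5.4), so the date of censoring carries prognostic information. Kaplan-Meier treats a censored participant as having the same outlook as those still observed, who are mostly still on drug. If mortality rises after stopping, the estimated OS is too high.

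Module A dose escalation has a smaller, related gap. Participants still on drug when Amendment 3 was approved remain observed while treated and are lost once they stop. The SAP has no rule for this.

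**Working it through.** **1. The group affected.** The plan's counts reproduce:
- Module B escalation: 3 cohorts × 9 = 27.
- Module B: 27 + 3 × 16 = 75.
- Module A: 27 + 5 × 16 = 107.
- Total: 107 + 75 = 182.

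Module B escalation is therefore up to 27 of 75 participants (36%).

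**2. The passages side by side.**

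| Place | Module A escalation | Module A expansion | Module B escalation | Module B expansion |
|---|---|---|---|---|
| Synopsis (both entries), 4.1, 9.17, 11.1.2, SAP 3.1 | until Amendment 3 | 2 years | not mentioned | 2 years |
| Appendix 1 | until Amendment 3 | 2 years | 2 years | 2 years |

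The only difference is Module B escalation. The Module B schedule labels other rows as expansion only (T-cell repertoire, serum biomarkers), so an intended limit on the survival row would be expected to appear there too.

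**3. Size.** The documents give no survival rates or hazards, so everything in this step is assumed. Let λ be the rate of stopping treatment, h the death hazard on drug, m the death hazard after stopping, g the time from stopping to last contact, and a = λ + h − m. With constant hazards:
- True survival: S(t) = e^(−(λ+h)t) + (λ/a)(e^(−mt) − e^(−(λ+h)t)).
- With no contact beyond g, the ratio of recently stopped to on-drug participants still under observation is ρ = λ(e^(ag) − 1)/a for t > g. The observed hazard is (h + mρ)/(1 + ρ), and KM(t) = S(g)·exp[−(t − g)(h + mρ)/(1 + ρ)].

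Worked case: median time to stopping 3 months (λ = 0.2310), on-drug hazard equal to a 24-month median (h = 0.0289), 8-month median after stopping (m = 0.0866), g = 30 days = 0.986 months.
- a = 0.1733.
- S(12) = 0.0442 + (0.2310/0.1733)(0.3536 − 0.0442) = 0.457.
- ρ = 0.2310 × (1.1863 − 1)/0.1733 = 0.248.
- Observed hazard = (0.0289 + 0.0866 × 0.248)/1.248 = 0.0404 per month.
- KM(12) = 0.966 × exp(−11.014 × 0.0404) = 0.62.

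The estimate is 62% against a true 46%, about 16 points too high. If 40% stop without confirmed progression and stay in contact, the estimate is 50%.

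Two sets of assumptions gave these overstatements in percentage points:

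| Assumptions | Contact after stopping | 6 months | 12 months |
|---|---|---|---|
| Mean time on drug 3 or 5 months; on-drug hazard 2–4% per month; median after stopping 6–9 months; g = 1 month | none | about 4 to 11 | 10 to 24 |
| Same | 30% stop without progression and stay in contact | – | about 3 to 10 |
| Median time to stopping 3 or 5 months; on-drug median 24 or 48 months; median after stopping 5, 8 or 12 months; g = 30 days | none | about 3 to 13 | 8 to 29 |
| Same | 20% or 40% stop without progression and stay in contact | 1 to 9 | about 2 to 16 |

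If h = m, the bias is zero. If mortality falls after stopping (implied medians of 8 months on drug and 12 months after, median time to stopping 4 months), 12-month OS comes out about 6 points too low.

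**4. Sampling error for comparison.** With 27 participants, complete follow-up and a 50% rate, the 95% half-width is 1.96 × √(0.25/27) = 0.19, or about 19 points.

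**The case against.** **Sites may follow Appendix 1 anyway.** Protocol section 9 sends them there for the timing of procedures, and the body text is silent on Module B escalation rather than excluding it. This is fair, and the loss may never occur. But the survival row points back to 9.17, which covers expansion only, so Appendix 1 does not settle the matter.

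**Follow-up is not lost for everyone.** Protocol 11.1.1 keeps 3-monthly contact about response and survival, as applicable and in any phase, for participants who stop for reasons other than confirmed progression. This stands and roughly halves the illustrative bias or better. It leaves out those who stop for progression.

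**The consequence is small.** OS is exploratory, its results may be left out of the study report, and no sample size or dose decision uses it. That also stands, and sampling error alone is about 19 points either way.

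**Module A escalation follow-up ended by explicit decision**, stated the same way throughout. For participants already off drug, that is censoring by calendar date. The concern touches only those of the 26 treated who were still on drug at approval, a number the documents do not give.

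A reader might infer two stronger points that the documents do not support:
- *OS is censored when treatment stops.* That would give 11 to 49 points at 12 months under the second set of assumptions. SAP 6.7.2.3 censors at the last date known alive, which can reach the end-of-treatment visit or later.
- *Escalation and expansion, or the two modules, are pooled in one OS curve.* SAP 6.1 combines dose-level cohorts and lists expansion cohorts separately. Protocol 14 analyses monotherapy and combination separately. No pooled curve is planned.

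**Conclusion.** The contradiction is established from the text: Module B dose escalation has 2-year survival follow-up in Appendix 1 and none in the synopsis, Protocol 4.1, 9.17, 11.1.2 or SAP 3.1. Up to 27 participants are affected.

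If sites follow the body text, OS in that phase is subject to informative censoring, mainly of those who stop for progression, and the 6- and 12-month rates are probably too high. It would go too far to say that they are too high. The direction requires higher mortality after stopping than on drug, which is plausible in relapsed or refractory cancer but is not quantified in the documents.

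On that assumption, the illustrative 12-month overstatement is about 10 to 24 points with no post-treatment contact (8 to 29 under the wider assumptions), and about 2 to 16 points with the contact in 11.1.1. The endpoint is exploratory, so this is worth correcting because it is cheap and because contacts not made may not be recoverable. It does not threaten the primary objective.

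**What to change.** Reconcile the passages. The preferred route is to add Module B dose escalation to the survival follow-up text in both synopsis entries, Protocol 4.1, 9.17 and 11.1.2, and SAP 3.1, so that they match Appendix 1. The cost is wording in six places, plus quarterly contacts, which may be by telephone, for up to 27 participants. Appendix 1 already schedules these contacts.

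If the sponsor intends no such follow-up, correct Appendix 1 instead. Then either omit OS rates for Module B escalation or report them with a statement that censoring is informative and the rates are probably too high.

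For Module A dose escalation, state in SAP 6.7.2.3 that OS is cut off at the Amendment 3 approval date. Participants not known to have died by then are censored at the last date known alive on or before it. Participants on drug at that date are then not censored by stopping treatment. The downside is that a few later deaths are not used.

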#### 4.1.1 Dose Escalation Phase

The goal of the Dose Escalation Phase of this study is to initially characterize the safety and tolerability of MGC018 administered alone or in combination with MGA012 and, more specifically, to define the MTD of these respective monotherapy and combination regimens. If no MTD is defined during the dose escalation of MGC018 monotherapy (Module A) after escalation to the maximum protocol-specified dose, then that dose level will be designated as the MAD for MGC018 monotherapy. Similarly, if no MTD is defined during dose escalation of the combination of MGC018 and MGA012 (Module B), after escalation to the maximum protocol-specified dose, then that dose level will be designated as the MAD for MGC018 and MGA012 combination therapy.

For the purposes of guiding decisions regarding dose escalation, the **DLT Evaluation Period** for Module A (monotherapy) will be 21 days following administration of the first dose of MGC018. For Module B (combination therapy), the DLT evaluation period will be 42 days in duration.

Dose escalation will follow a conventional 3+3+3 design: successive cohorts of 3 to 9 participants each will be evaluated in sequential escalating doses of MGC018 administered alone (Module A) or in combination with MGA012 (Module B) as shown below (**Table 3** and **Table 4**).

Sentinel dosing will be used for the first 2 dose levels. The first administration of MGC018 in participants in the first 2 dose levels in Module A will be staggered by at least 48 hours.

In Module B, MGA012 will be administered at a dose of 375 mg (flat dose) Q3W, beginning on Day 22 of Cycle 1, and continuing on Days 1 and 22 of every cycle thereafter.

Participants who require dose delays greater than 21 days secondary to AEs considered unrelated to study treatment or any other cause unrelated to study treatment are considered unevaluable for safety and toxicity during the DLT evaluation period and will be replaced.

Intermediate dose levels may be explored based on review of the cumulative safety data and upon agreement between the investigators and the sponsor.

